## PATIENT REPORTED OUTCOMES (QUALITY OF LIFE)

QOL will be measured using the PROs of EORTC QLQ-C30, EORTC QLQ-LC13, the DLQI, and the EQ-5D. 15-17

The EORTC questionnaires will be scored using the published scoring algorithms provided by the EORTC. For each item or scale, a linear transformation will be applied to standardize the raw score to a range from 0 to 100. A high scale score represents a higher response level.

Thus a **high score for a functional scale** represents a *high / healthy level of functioning*, a **high score for the global health status / QOL** represents a *high QOL*, but a **high score for a symptom scale / item** represents a *high level of symptomatology / problems*.

The baseline PRO measurement will be defined as the last value prior to or on the day of the first dose of CO-1686 or erlotinib. The on-treatment period will be defined as the day after the first dose of CO-1686 or erlotinib to 28 days after the last dose of protocol-specified treatment. QOL measurements collected during the on-treatment period will be included in the summary tables.

The summary of PRO data will include descriptive statistics (N, mean, standard deviation, minimum, median, and maximum) of the observed measurements at each visit during the on-treatment period. Summaries using descriptive statistics of the change or percent change from baseline to each visit during the on-treatment period may also be provided. Graphical presentations may be used to present the mean changes over time.

The time to a worsening in symptoms will be computed as 1+ the number of days from the date of randomization to the first instance of  $a \ge 10$  point increase from baseline in symptoms. Patients without an event will be censored on the date of their last assessment. Kaplan-Meier methodology will be used to summarize the time deterioration and the treatment groups will be compared using the logrank test and hazard ratio.

Analyses of changes and/or percent changes from baseline will be analyzed for each scheduled post-baseline visit and for the final visit for the EQ-5D instrument and the EQ-VAS. If more than one measurement exists for a patient on a particular day, then an arithmetic average will be calculated. This average will be considered to be that patient's measurement for that day. Post-baseline measurements more than 28 days after the last dose of protocol-specified treatment will not be included. Patients that do not have both a baseline measurement and at least one post-baseline measurement will not be included.

At a given visit, the change and/or percent change from baseline will be compared between the randomized treatment groups using an analysis of covariance (ANCOVA), using the treatment as a categorical factor and baseline measurement for the parameter as a continuous covariate.

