## 5 STUDY DESIGN

# 5.1 Overall Study Design and Plan

This is a randomized, open-label, Phase 2/3 study of CO-1686 versus erlotinib as a first-line treatment for patients with advanced/metastatic NSCLC whose tumors have EGFR-activating mutations. The study will consist of Phase 2 and Phase 3 parts which will use the same enrollment criteria and treatment assignment principles. The Phase 2 part is an open-label study; in the Phase 3 part, the sponsor will be blinded to efficacy and safety results aggregated by randomized treatment group. The Phase 2 part will enroll approximately 200 patients. Data from the Phase 2 part will be used to inform on the sample size in the Phase 3 part of the study. The sample size of the Phase 3 component will be capped at approximately 1,000 patients. The Phase 3 part will include up to 3 interim analyses. At each interim analysis, enrollment into the Phase 3 part may be stopped if there is a high probability of success in the Phase 3 part of the study. If enrollment is stopped early, the Phase 3 part of the study will continue until at least 70% of the randomized patients have a PFS event.

Patients will be stratified for randomization according to the followings factors:

- Sensitizing EGFR mutation (L858R, del19, or other)
- Territory of residence at time of randomization (Asia or non-Asia)

Patients will be randomized in a 1:1 ratio to Treatment Arm #1 or #2:

- Treatment Arm #1 CO-1686, 500 mg orally (PO), with food, BID
- Treatment Arm #2 erlotinib, 150 mg PO, on an empty stomach, once daily (QD)

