### 5.1.2 Treatment Period

Patients will receive either CO-1686 or erlotinib. The sponsor will be blinded to efficacy and safety results aggregated by randomized treatment group in the Phase 3 part of the study. CO-1686 will be administered to patients as 500 mg PO tablets on a BID basis with a meal or within 30 minutes after a meal (see Section 7.3). Erlotinib will be taken 150 mg PO QD on an empty stomach; i.e., at least 1 hour before or 2 hours after the ingestion of food (see Section 7.3). Treatment with CO-1686 or erlotinib is continuous. Dosing will be delayed or reduced according to protocol-specified toxicity criteria (See Section 7.4).

Patients will undergo serial assessments for anti-tumor efficacy, drug safety, PK, PRO, and biomarkers. Sparse blood sampling for population PK analyses will be conducted in all patients initially randomized and treated with CO-1686. Serial blood sampling for longitudinal quantitative assessment of ctDNA will be conducted on all patients in the study. All patients will provide a tumor biopsy during screening for determination of EGFR mutation status. For both the Phase 2 and 3 parts, local laboratory testing will be used to determine the presence of an activating EGFR mutation. EGFR mutation status will be confirmed by central testing retrospectively.

ECGs will be performed and interpreted locally for patient care decisions; however, tracings will be collected centrally for independent evaluation. Tissue and blood specimens from both treatment arms will be used to explore biomarkers that may be predictive of response or primary resistance to CO-1686 and/or erlotinib. AEs will be collected from the time the first dose of CO-1686 or erlotinib is administered through 28 days after the last dose. Local laboratories will be used for hematology, chemistry, and urinalysis.

QOL questionnaires (EORTC QLQ-C30, EORTC QLQ-LC13, the DLQI, and the EQ-5D) will be collected at screening, predose on C1D1, then every  $8 \pm 1$  weeks for the first 6 months (Day 1 of Cycles 3, 5, 7); after Cycle 7, questionnaires will be collected every  $12 \pm 1$  weeks (Day 1 of Cycles 10, 13, 16, etc.) and at end-of-treatment. In the Phase 2 part only, patients participating in the crossover portion will be asked to complete QOL questionnaires mirroring the on-study assessment schedule.

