# 7.2 Method of Assigning Patients to Treatment Groups

Following confirmation of patient eligibility by the sponsor, patients will be centrally randomized in the ratio 1:1 to receive oral CO-1686 or erlotinib. Patients will be stratified according to presence of sensitizing EGFR mutation (L858R, del19, or other) and territory of residence at time of randomization (Asia vs non-Asia).

The treatment assignment will be generated using the following procedure to ensure that treatment assignment is unbiased. A patient randomization list will be produced by the Interactive Voice/Web Response System (IVRS/IWRS) provider using a validated system that automates the random assignment of treatment. The investigator or his/her delegate will call or log on to the IVRS/IWRS and confirm that the patient fulfills all the inclusion/exclusion criteria. Each package of study drug will contain the unique identification code containing the LOT number and a space for the site to enter the "Subject ID".

Treatment should be initiated on C1D1, which must occur within 3 days (72 hours) of randomization.

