Abbreviations: AAG = alpha-1 acid glycoprotein; ALT = alanine aminotransferase; ANC = absolute neutrophil count; AST = aspartate aminotransferase; β-hCG = beta human chorionic gonadotropin; BUN = blood urea nitrogen; CT = computed tomography; ECG = electrocardiogram; ECOG = Eastern Cooperative Oncology Group; EGFR = epidermal growth factor receptor; EORTC QLQ-C30 = European Organization for the Research and Treatment of Cancer Quality of Life Questionnaire, Core 30; EORTC QLQ-LC13 = European Organization for the Research and Treatment of Cancer Quality of Life Questionnaire, Lung Cancer 13; MRI = magnetic resonance imaging; RECIST = Response Evaluation Criteria in Solid Tumors; WBC = white blood cells

- a CO-1686 will be administered PO at 500 mg BID, with a meal or within 30 minutes after a meal and erlotinib will be administered PO QD at 150 mg on an empty stomach (1 hour before or 2 hours after ingesting food)
- b Unless specified, procedure is completed ± 1 day of scheduled time point and is synchronized with C1D1 of CO-1686 or erlotinib.
- c C1D1 and randomization can be the same day, but not required. C1D1 must be within 3 days of randomization. Procedures required on C1D1 may be omitted if completed ≤ 3 days earlier during the screening period.
- Fasting glucose required on  $C1D4 \pm 1$  day,  $C1D8 \pm 1$  day,  $C1D15 \pm 1$  day, and  $C2D15 \pm 1$  day for patients taking CO-1686 only. Not required for patients taking erlotinib.
- Vital signs (blood pressure, pulse, and temperature) taken predose on C1D1 and without reference to dose at every subsequent visit. All vital signs will be obtained after the patient has been resting for at least 5 min. Height is only required once at screening. Weight is measured at each visit.
- f On C1D1 concomitant medications and procedures will be monitored pre- and postdose.
- g Patients are to continue using double-barrier contraception for 12 weeks after last dose of CO-1686 and 2 weeks after the last dose of erlotinib and report any pregnancies during this period.
- h Serum β-hCG (evaluated by local labs) will be performed only on women of childbearing potential ≤ 3 days prior to C1D1 and at end-of-treatment. If the serum pregnancy test results are not available on Day 1, a urine pregnancy test can be performed on C1D1 to confirm that the patient is not pregnant prior to dosing.

Table 9-1: Schedule of Assessments in Phase 2 (Before Crossover) and in Phase 3 (Cont.)

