# 9.1 Screening Period

Following written informed consent, and unless otherwise specified, the following assessments should be performed during the 35-day period prior to the first dose of study treatment. Obtaining written informed consent does not signify the start of the screening period. The first screening activity performed after signature of the ICF begins the 35-day screening period. If a biopsy was performed within 60 days of C1D1, and no intervening treatment was given, a repeat biopsy is not required if adequate tumor tissue can be provided for mutational analysis and biomarker research. Assessments performed prior to patient signing informed consent are acceptable only if confirmed to have been standard of care. Unless otherwise specified, if a procedure is completed more than 35 days prior to the first day of dosing it will need to repeated prior to C1D1. C1D1 and randomization can be the same day, but are not required to be the same day. C1D1 must occur within 3 days after date of randomization.

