## To be performed $\leq$ 14 days prior to Cycle 1 Day 1:

- Physical examination by body system
- ECOG performance status
- Vital signs (blood pressure, pulse, and temperature), height, and weight
- Hematology (hemoglobin, hematocrit, WBC and differential [with ANC], platelet count, and reticulocyte count) ≤ 14 days prior to the first day of dosing (C1D1)
- *Fasting* serum chemistry (total protein, albumin, creatinine, blood urea nitrogen [BUN] or urea, total bilirubin, alkaline phosphatase, ALT, AST, fasting glucose, sodium, potassium, magnesium, chloride, bicarbonate [CO₂], calcium, phosphorus, total cholesterol and hemoglobin A1c [HbA1c]) ≤ 14 days prior to the first day of dosing (C1D1)
- Urinalysis performed on freshly voided clean sample (dipstick for protein, glucose, blood, pH, and ketones) ≤ 14 days prior to C1D1. If dipstick findings are abnormal based on investigator judgment, then a microscopic evaluation will be performed to assess the abnormal findings
- Study procedure-related AEs
- 12-lead ECG (in triplicate, 10-sec tracings > 2 min apart)
- QOL questionnaires (EORTC QLQ-C30, EORTC QLQ-LC13, the DLQI, and the EQ-5D)

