## To be performed $\leq 3$ days prior to Cycle 1 Day 1:

• Serum pregnancy test (by local laboratory) ≤ 3 days prior to C1D1 for women of childbearing potential. If the serum pregnancy test results are not available on Day 1, a urine pregnancy test can be performed on C1D1 to confirm that the patient is not pregnant prior to dosing. Both values should be entered in the eCRF.

At the end of screening, patients will be randomized to treatment with CO-1686 or erlotinib (see Section 7.2).

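### The PRO baseline rule by default selects the C1D1 questionnaire, which can follow open-label randomisation, although a pre-randomisation questionnaire is already collected

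*Combined protocol and SAP*

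**What the plan says.** The baseline rule is in the patient-reported outcomes part of Section 11.2.4.2: "The baseline PRO measurement will be defined as the last value prior to or on the day of the first dose of CO-1686 or erlotinib". Section 5.1.2 gives the collection times: the questionnaires "will be collected at screening, predose on C1D1, then every" eight weeks. Section 9.1 places the first set ("QOL questionnaires (EORTC QLQ-C30, EORTC QLQ-LC13, the DLQI, and the EQ-5D") within the 14 days before C1D1.

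On allocation, Section 9.1 states: "At the end of screening, patients will be randomized to treatment with CO-1686 or erlotinib". Section 7.2 adds: "Treatment should be initiated on C1D1, which must occur within 3 days (72 hours) of randomization". Section 9.1 also allows both on one day: "C1D1 and randomization can be the same day, but are not required to be the same day". Table 9-1, footnote c, contains an omission rule: "Procedures required on C1D1 may be omitted if completed ≤ 3 days earlier during the screening period".

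Section 5.1 describes the design: "This is a randomized, open-label, Phase 2/3 study of CO-1686 versus erlotinib". In Phase 3, Section 7.6 blinds only the sponsor, and only to results aggregated by arm.

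**The concern.** A baseline is protected by randomisation only if it is recorded before the allocation can influence it. Quality-of-life scores are subjective. A patient who has just learned the assigned drug may answer differently out of relief or disappointment, and differently in the two arms. If that answer becomes the reference value, an arm difference enters the comparison before any drug has been taken.

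Change from baseline in QOL is a listed secondary endpoint (Section 4.2.2). The rule also fits poorly with the time-to-worsening analysis: its clock starts at randomisation, yet its reference score may be recorded after that. The plan collects a score that avoids the problem, does not use it when a C1D1 form exists, and specifies no sensitivity analysis based on it.

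**Working it through.** The plan states no SD, correlation, significance level or power for QOL, so there is no figure to reproduce. The check is of timing first, then of possible size.

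**Step 1: which form the rule picks**

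| Situation | Form selected | Relation to randomisation |
|---|---|---|
| Forms at screening and C1D1; C1D1 on a later day than randomisation (up to 72 hours) | C1D1 | After |
| Forms at both; randomisation and C1D1 on the same day | C1D1 | Not determinable; no order is stated |
| C1D1 form omitted because screening forms were done within 3 days before | Screening | Before |

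The default is the C1D1 form. The documents do not give the share of patients in each row.

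**Step 2: which analyses use it** (Section 11.2.4.2)

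- Time to a symptom increase of at least 10 points from baseline (logrank, hazard ratio): yes.
- ANCOVA of change, which follows directly on the EQ-5D and EQ-VAS paragraph: yes, in both outcome and covariate.
- Summaries of change or percent change, which are optional: yes.
- Summaries of observed scores at each visit: no.

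**Step 3: possible size, illustration only**

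From the documents: n = about 100 per arm in Phase 2 and up to 500 in Phase 3 (Section 6.1). Assumed: no true effect; a mean baseline shift d (in SD units) in one arm that is gone by follow-up; correlation ρ between baseline and follow-up; two-sided 0.05; normal approximation. Because d is the average over the arm, if only a share p of its patients shift, each by δ, then d = pδ.

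- Raw change: bias d, SE = √(2(1−ρ)) × √(2/n).
- ANCOVA: bias ρd, SE = √(1−ρ²) × √(2/n).
- False-positive rate = Φ(−1.96 + bias/SE) + Φ(−1.96 − bias/SE).

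Example, ANCOVA with d = 0.1, ρ = 0.5, n = 500: bias = 0.05; SE = 0.866 × 0.0632 = 0.0548; ratio = 0.913; rate = Φ(−1.047) + Φ(−2.873) = 0.150.

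False-positive rate at a single visit:

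| n per arm | ρ | d | ANCOVA | Raw change |
|---|---|---|---|---|
| 100 | 0.5 | 0.05 | 0.055 | 0.064 |
| 100 | 0.5 | 0.1 | 0.069 | 0.109 |
| 100 | 0.5 | 0.2 | 0.129 | 0.293 |
| 100 | 0.7 | 0.1 | 0.107 | 0.150 |
| 500 | 0.5 | 0.05 | 0.074 | 0.124 |
| 500 | 0.5 | 0.1 | 0.150 | 0.353 |
| 500 | 0.5 | 0.2 | 0.447 | 0.885 |
| 500 | 0.7 | 0.1 | 0.341 | 0.532 |

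ANCOVA reduces the bias but does not remove it.

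For worsening on a 0 to 100 symptom scale, the single-visit probability with a baseline reported s points too high is 1 − Φ((10 + s)/(SD√(2(1−ρ)))). With assumed SD 20 and ρ = 0.5 the divisor is 20, so s = 0 gives 1 − Φ(0.5) = 0.309 and s = 2 gives 1 − Φ(0.6) = 0.274. Over SD 20 to 25 and ρ 0.5 to 0.7, the range moves from 0.26–0.35 to 0.22–0.32.

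With a baseline taken before randomisation, d = 0 by design and this source of bias disappears.

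**The case against.** The strongest objection is that disclosure may also shift follow-up scores. If a fraction f of the shift d persists, the error in raw change is −(1−f)d with the C1D1 baseline and +fd with the screening baseline, so the screening baseline does worse once f exceeds 0.5. For ANCOVA the errors are (f−ρ)d and fd, so at ρ = 0.5 the crossover is f = 0.25. The arithmetic is right, and it limits any claim about net benefit. But persistent reporting bias in follow-up scores is a separate open-label problem. A post-randomisation baseline offsets it only by chance, and that is not a reason to choose one.

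Three further points stand in part:

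- The last pre-treatment value is the plan's general convention, used also for laboratory values and vital signs (Sections 11.2.5.3 and 11.2.5.4). That explains the wording. Self-reported scores, however, are more open to influence from a known allocation.
- The practical stakes are reduced. Development has been discontinued, Appendix D closes enrolment, and its Table 4 schedules no QOL questionnaires. Section 11 still specifies these analyses, and the point applies to data already collected.
- Changing the baseline could lose patients who lack a screening form: Section 11.2.1 rules out imputation, and Section 11.2.4.2 drops patients without a baseline from the EQ-5D analyses. This is a fair criticism of a change made without a fallback.

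A reader might also infer that every patient's baseline is recorded after a known allocation. The documents do not support that: the omission rule and same-day randomisation both allow otherwise, and no section says when the patient is told the arm.

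**Conclusion.** The point holds as a weakness in the definition. The rule admits a baseline recorded after a known allocation, makes the C1D1 form the default, mixes pre- and post-randomisation values in unknown proportion, and leaves an available pre-randomisation score unused. The analyses exposed are time to worsening, the EQ-5D/EQ-VAS ANCOVA and any change-from-baseline summaries.

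Two stronger conclusions are not supported. The first is that all QOL results are affected: the observed-score summaries do not use baseline. The second is that a bias of a particular size is present. Nothing in the documents shows that a shift occurred, or which way it would go, and d, ρ and the SDs above are assumptions. The 0 to 100 scoring is given for the EORTC questionnaires, whereas the ANCOVA is set out for EQ-5D and EQ-VAS, so a bias in EORTC points should not be read across to it. The results in SD units show only that a modest shift could matter more at 500 per arm than at 100, provided it does not persist.

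This is a cheap improvement. It affects secondary endpoints only; the primary endpoint, investigator-assessed PFS, is untouched.

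**What to change.** In Section 11.2.4.2, for all four instruments and every baseline-referenced analysis:

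1. Define PRO baseline as the last questionnaire completed before randomisation, normally the screening form.
2. Where C1D1 and randomisation fall on the same day and the order cannot be established, use the screening form.
3. Where no pre-randomisation form exists, use the predose C1D1 form, so that no patient is lost. Report how many patients per arm rely on this.
4. Report the current C1D1-based definition as a sensitivity analysis.

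The cost is a change of wording and some derivation rules; the screening forms are already collected and no sample-size figure changes. Rule 2 avoids relying on questionnaire completion times, which the documents do not say are recorded. The downside is a baseline up to about 14 days older, in both arms alike. The change does not address open-label influence on follow-up scores, which should be acknowledged when the results are interpreted.

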#### 11.2 Statistical Methods

#### 11.2.1 General Considerations

Quantitative variables will be summarized using descriptive statistics (N, mean, standard deviation, median, minimum, and maximum) and/or frequency and percentages for medically relevant categories. Categorical variables will be presented using frequencies and percentages.

Kaplan-Meier methodology will be used to summarize time-to-event variables. The number of patients with events and the number of censored patients will also be presented. The stratified logrank test will be used to compare the time-to-event distributions between the randomized treatment groups. The same variables used to stratify the randomization will be used in the stratified analyses. In addition, the Cox proportional hazards model will be used to estimate the HR between the randomized treatment groups.

The Fisher's Exact Test will be used to compare frequencies between treatment groups and the t-test will be used for comparing means between treatment groups.

All data will be used to their maximum possible extent but without any imputations for missing data. Results from Phase 2 and Phase 3 will be presented separately and pooled.

All statistical analyses will be conducted with the statistical analysis software (SAS®) system, Version 9.1 or higher.

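### EQ-5D change is tested by a separate ANCOVA at each visit, so interim scores of patients who stop treatment do not inform later comparisons; a repeated-measures model would be a cheap, modest improvement

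*Combined protocol and SAP*

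**What the plan says.** Section 11.2.4.2 (Patient Reported Outcomes) of the combined protocol and SAP analyses change from baseline "for each scheduled post-baseline visit and for the final visit for the EQ-5D instrument and the EQ-VAS". At a given visit the change "will be compared between the randomized treatment groups using an analysis of covariance (ANCOVA"), with arm as a factor and the baseline value as the only covariate. No other term is listed, and the final visit is not defined.

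Two restrictions apply: "Post-baseline measurements more than 28 days after the last dose of protocol-specified treatment will not be included". In addition, a patient needs a baseline value and one or more later values to enter the analysis. Section 11.2.1 adds a general rule: "All data will be used to their maximum possible extent but without any imputations for missing data".

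Section 9.6.5 schedules questionnaires at Cycles 3, 5 and 7, then Cycles 10, 13, 16 and so on, and at end of treatment. Section 9.5 lists none during follow-up. No section gives a repeated-measures model, a missing-data assumption or a sensitivity analysis for questionnaire dropout.

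**The concern.** Under Section 12.1 progression normally ends treatment, so stopping is plausibly linked to health. Take a patient whose scores fall at Cycles 3 to 7 and who then stops. The Cycle 10 and 13 tests contain no value for that patient and make no use of the decline already recorded. Each test is unbiased for the mean of all included patients only if, given arm and baseline, being observed is unrelated to the interim scores. If stopping follows those scores, the patients left at later visits are a selected group, and the selection may differ by arm.

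Precision is also lost, because interim scores are correlated with the missing later ones. That sits badly with the stated aim of using the data as fully as possible. At stake is the reading of late-visit EQ-5D and EQ-VAS differences, which are a secondary endpoint.

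**Working it through.** **The plan's own figure.** No sizing is given for EQ-5D. The only sizing figure is in Section 11.3: 640 PFS events for about 80% power at HR 0.80 and one-sided 0.025.
- Schoenfeld: 4 × (1.960 + 0.842)² / (ln 0.80)² = 631 events.
- Freedman: (1.960 + 0.842)² × (1.80/0.20)² = 636 events.
- Power at 640 events: Φ(√640 × 0.2231/2 − 1.960) = 80.6%.

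The figure reproduces, and nothing below changes it.

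**Attrition.** Inputs are median PFS of 10 months (erlotinib) and 13 months (CO-1686) from Section 11.3, and 28-day cycles. Assumptions are exponential times and treatment ending at progression. The share on treatment at Day 1 of cycle c is 0.5^(t/median), with t = (c − 1) × 28/30.44 months.

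| Cycle | t (months) | Erlotinib | CO-1686 |
|---|---|---|---|
| 3 | 1.8 | 88% | 91% |
| 5 | 3.7 | 78% | 82% |
| 7 | 5.5 | 68% | 75% |
| 10 | 8.3 | 56% | 64% |
| 13 | 11.0 | 47% | 56% |
| 16 | 13.8 | 38% | 48% |

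By Cycle 13 about half of those randomized would have a value, with a gap of about 9 points between arms.

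**Bias and precision.** A simulation compared visit-wise ANCOVA with a direct-likelihood repeated-measures model (visit-by-arm and visit-by-baseline terms, covariance taken as known). It used 500 patients per arm, 400 runs per setting, visits at Cycles 3, 5, 7, 10 and 13, and no data after dropout. These inputs are not in the documents and are assumed: unit SD; correlation 0.6 (compound symmetry) or 0.8 (autoregressive); log-hazard of dropout 0 to 1.0 per SD of score. Bias is measured against the mean had every patient stayed on treatment. A negative sign makes CO-1686 look worse. Monte Carlo error is about 0.004 SD.

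| Dropout depends on | ANCOVA bias at Cycle 13 (SD) | Repeated-measures bias (SD) |
|---|---|---|
| Nothing | about 0 | about 0 |
| Last score, equally in both arms | −0.02 to −0.035 | at most 0.01 in size |
| Last score, twice as strongly on erlotinib | −0.08 to −0.14 | at most 0.01 in size |
| Last score, on CO-1686 only | +0.06 to +0.11 | at most 0.01 in size |
| Unseen current score, equally in both arms | −0.03 to −0.05 | −0.015 to −0.03 |

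Set against the simulated ANCOVA standard error at Cycle 13, the largest equal-dependence bias with no true difference is 0.035/0.084 = 0.4 standard errors. The largest unequal one is 0.137/0.080 = 1.7 standard errors. In that last setting the simulated shares remaining were 48% and 62%, a wider gap than in the attrition table.

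The model-based variance ratio, ANCOVA to repeated measures, is about 1.01 to 1.08 at Cycle 7 and 1.07 to 1.19 at Cycle 13. Taking square roots at Cycle 13, the ANCOVA standard error is about 3 to 9% larger. Empirical ratios over 400 runs are noisier (1.03 to 1.25). Because the covariance was taken as known, the gain is if anything slightly flattered.

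**The case against.** Several points on the other side stand.

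- **Patients who stop are not wholly excluded.** A reader might infer that EQ-5D is tested only in patients still on treatment, or that earlier scores are thrown away. Neither is so. Values up to 28 days after the last dose count, a final-visit analysis is planned, each interim score is tested at its own visit, and baseline is a covariate. But the final visit is undefined and does not repair the later by-visit tests. The End-of-Treatment Visit falls 28 ± 7 days after the last dose (Section 9.4), so its last week lies outside the cut-off.
- **The direction is not fixed.** A reader might infer that a drug which delays progression will look worse on quality of life. The simulated sign reverses when health-linked dropout occurs only on CO-1686, and the documents do not say how dropout depends on health in either arm.
- **The PFS hazard ratio is not a discontinuation rate.** Section 5.1.2 allows treatment, with questionnaires, after progression in both arms, and toxicity also ends treatment. The attrition figures are therefore illustrative.
- **The plan's target may be on-treatment.** The mixed model estimates a hypothetical mean for patients who have stopped. The plan does not state its target, so the word bias holds only relative to the mean had every patient stayed on treatment.
- **Practical reach is limited.** The Extension Phase schedule (Appendix D, Table 4) lists no questionnaires, and no further patients will be enrolled. The change can help only with data already collected.

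**Conclusion.** The point holds as a cheap improvement. The text supports four facts: by-visit ANCOVA on baseline and arm, a 28-day cut-off, no imputation, and no repeated-measures model. Interim scores of patients who stop therefore do not inform later comparisons.

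The size is modest: about 0.02 to 0.035 SD at Cycle 13 if dropout depends on the last score equally in both arms, up to about 0.14 SD if the dependence differs, and ANCOVA variance about 7 to 19% larger. These figures rest on the assumed correlation, dropout strength and exponential attrition; the documents fix none of them. The direction of bias cannot be claimed. EQ-5D is a secondary endpoint with no stated alpha or sizing, and the PFS conclusion is unaffected.

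**What to change.** Make the main EQ-5D and EQ-VAS comparison one mixed model for repeated measures, with arm, visit, arm-by-visit, baseline, baseline-by-visit and an unstructured covariance. Use all on-treatment scheduled visits and report the arm difference at each. State how End-of-Treatment values are assigned to visits. Keep visit-wise ANCOVA and the final-visit analysis, with final visit defined, as sensitivity analyses. Report numbers observed by visit and arm.

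The cost is SAP wording and standard software. The model imputes nothing, so it fits the rule in Section 11.2.1. Its downside is that it relies on missing at random and estimates a hypothetical on-treatment mean for patients who stopped. Because some bias remains when dropout follows the unseen score, a sensitivity analysis for data not missing at random would be a sensible addition; if it uses imputation, that rule needs a stated exception.
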